Start neoadjuvant radiotherapy	108290001 Radiat oncology AND, radiotherapy (procedure)	ion 373847000 /OR Neo-adjuvant - intent (qualifier value)	Date	439272007 Date of procedure (observable entity) 413946009 Date treatment started (observable entity)	
Adjuvant radiotherapy	108290001 Radiat oncology AND, radiotherapy (procedure)	ion 373846009 Adjuvant - /OR intent (qualifier value)	- Yes No Unknown	373066001 Yes (qualifier value) 373067005 No (qualifier value) 261665006 Unknown (qualifier value)	
Target volume: Chest wall	428624002 Radiotherapy chest v (procedure)	to vall	Yes	373066001 Yes (qualifier value) 373067005 No (qualifier value)	
Target volume: Interpectoral nodes	168522007 Radiotherapy lymphatic irradiat (procedure)	for ion	Yes	373066001 Yes (qualifier value)	

Data Element	Variable SNOMED code + FSN	Variable alternative SNOMED codes	Permissible values	Values SNOMED code + FSN	Values alternative SNOMED code + FSN	(additional)
	245274001 Interpectoral lymph node group (body structure)		No	373067005 No (qualifier value)		
Target volume: Internal mammary nodes	168522007 Radiotherapy for lymphatic irradiation (procedure) 245282001 Internal mammary lymph node group (body structure)		Yes No	373066001 Yes (qualifier value) 373067005 No (qualifier value)		
Total dose prescribed	399077005 Prescribed external beam radiation therapy dose (observable entity)		Gy	229029004 Gray (qualifier value)		
Number of fractions to elective regions	445232009 Boostradiationtherapy(procedure) 410673009 Region(attribute) 103390000 Elective(qualifier value)	228862004 Number of fractions (observable entity)	Number	260299005 Number (qualifier value)		
If boost, Fraction dose boost	445565002 Total boost radiation dose delivered (observable entity)		Gy	229029004 Gray (qualifier value)		

Data Element	Variable SNOMED code + FSN	Variable alternative SNOMED codes	Permissible values	Values SNOMED code + FSN	Values alternative (additional) SNOMED code + FSN
If boost, Number of fractions to boost regions	445232009 Boost radiation therapy (procedure)	228862004 Number of fractions (observable entity)	Number	260299005 Number (qualifier value)	
Dermatitis	49084001 Dermatitis	108290001 Radiation	Yes	373066001 Yes (qualifier value)	
	caused by radiation (disorder)	oncology AND/OR radiotherapy	No	373067005 No (qualifier value)	
		(procedure)	Unknown	261665006 Unknown (qualifier value)	
Lymphedem a	439128001 108290001 Radiation Lymphedema caused oncology AND/OR by radiation radiotherapy	Yes	373066001 Yes (qualifier value)		
	(disorder)	(procedure)	No	373067005 No (qualifier value)	
			Unknown	261665006 Unknown (qualifier value)	
Rib fracture	704169000 Pathological fracture of rib (disorder)	109301001 Radiation injury of bone (disorder)	Yes	373066001 Yes (qualifier value)	
		108290001 Radiation oncology AND/OR radiotherapy	No	373067005 No (qualifier value)	
	(procedur	(procedure)	Unknown	261665006 Unknown (qualifier value)	
Heart toxicity	430401005 Heart disease caused by	108290001 Radiation oncology AND/OR radiotherapy	Yes	373066001 Yes (qualifier value)	
	(disorder)	(procedure)	No	373067005 No (qualifier value)	
			Unknown	261665006 Unknown (qualifier value)	

Data Element	Variable SNOMED code + FSN	Variable alternative SNOMED codes	Permissible values	Values SNOMED code + FSN	Values alternative SNOMED code + FSN	(additional)
Radiation Pneumonitis	84004001 Radiation pneumonitis (disorder)	108290001 Radiation oncology AND/OR radiotherapy (procedure)	Yes	373066001 Yes (qualifier value)		
			No	373067005 No (qualifier value)		
			Unknown	261665006 Unknown (qualifier value)		
Hypertensio n	38341003 Hypertensive		Yes	373066001 Yes (qualifier value)		
	disorder, systemic		No	373067005 No (qualifier value)		
	arterial (disorder)		Unknown	261665006 Unknown (qualifier value)		
Smoking at the time of	77176002 Smoker (finding)		Yes	373066001 Yes (qualifier value)		
diagnosis			No	373067005 No (qualifier value)		
			Unknown	261665006 Unknown (qualifier value)		
Diabetes	73211009 Diabetes		Yes	373066001 Yes (qualifier value)		
	mellitus (disorder)	s (disorder)	No	373067005 No (qualifier value)		
			Unknown	261665006 Unknown (qualifier value)		
ВМІ	60621009 Body mass index (observable entity)	301331008 Finding of body mass index (finding)	Number	410680006 Number (attribute)		
Date of last follow up	185353001 Appointment date (finding)	308273005 Follow-up status (finding)	Date	410671006 Date (attribute)		

Data Element	Variable code + FSN	SNOMED	Variable alternative SNOMED codes	Permissible values	Values SNOMED code + FSN	Values alternative (additional) SNOMED code + FSN
Status at last follow up	308273005 Follow-up (finding)	status		Alive with no evidence of disease	438949009 Alive (finding) 51231003 Disease condition determination, cured (finding)	
				Alive with disease, index tumour successfully salvaged	438949009 Alive (finding)	
				Alive with disease, index tumour not salvaged	438949009 Alive (finding)	
				Died from intercurrent disease	419099009 Dead (finding)	184305005 Cause of death (observable entity) (other disorder than 372064008 Malignant neoplasm of female breast (disorder))
				Died from index tumour	419099009 Dead (finding)	184305005 Cause of death (observable entity) 372064008 Malignant neoplasm of female breast (disorder)
				Died from toxicity	419099009 Dead (finding)	184305005 Cause of death (observable entity) 373866000 Death due to chemotherapy toxicity (event)
				Died from unknown cause	419099009 Dead (finding)	184305005 Cause of death (observable entity) 261665006 Unknown (qualifier value)
Local 314955001 Local recurrence of		Yes	373066001 Yes (qualifier value)			
	breast (disor	der)		No	373067005 No (qualifier value)	

-	-	-	-	-	-
Data Element	Variable SNOMED code + FSN	Variable alternative SNOMED codes	Permissible values	Values SNOMED code + FSN	Values alternative (additional) SNOMED code + FSN
If YES, date of local recurrence	314955001 Local recurrence of malignant tumor of breast (disorder)		Date	410671006 Date (attribute)	
Regional recurrence	25173007 Recurrent neoplasm (disorder)	25173007 Recurrent tumor (finding) 312500006 Regional lymph node structure (body structure) 94392001 Secondary malignant neoplasm of lymph node (disorder)	Yes	373066001 Yes (qualifier value)	
			No	373067005 No (qualifier value)	
If YES, date of regional recurrence	25173007 Recurrent neoplasm (disorder)	25173007 Recurrent tumor (finding) 312500006 Regional lymph node structure (body structure) 94392001 Secondary malignant neoplasm of lymph node (disorder)	Date	410671006 Date (attribute)	
Distant metastases	128462008 Metastatic malignant neoplasm (disorder)	399409002 Distant metastasis present (finding)	Yes	373066001 Yes (qualifier value)	
			No	373067005 No (qualifier value)	
If YES, date of distant metastases	128462008 Metastatic malignant neoplasm (disorder)	399409002 Distant metastasis present (finding)	Date	410671006 Date (attribute)	

Data Element	Variable SNOMED code + FSN	Variable alternative SNOMED codes	Permissible values	Values SNOMED code + FSN	Values alternative (additional) SNOMED code + FSN
Postoperativ 60631000210103 e Breast cancer multidisciplinary	262061000 Postoperative period (qualifier value)	Yes	373066001 Yes (qualifier value)		
nary team meeting	meeting (procedure)		No	373067005 No (qualifier value)	
Preoperative multi-discipli nary team	Preoperative multi-discipli nary team meeting60631000210103 (Breast cancer F multidisciplinary va meeting (procedure))	262068006 Preoperative (qualifier value)	Yes	373066001 Yes (qualifier value)	
meeting			No	373067005 No (qualifier value)	
Was cancer 268547008 found in Screening for malignant neoplasm	243878006 Breast neoplasm screening status (finding)	Yes	373066001 Yes (qualifier value)	185710003 Breast screening abnormal - told patient (finding)	
	of breast (procedure)		No	373067005 No (qualifier value)	185713001 Breast screening non-attender (finding)
ls patient receiving	362964009 Palliative procedure		Yes	373066001 Yes (qualifier value)	
palliative treatment?	(procedure)		No	373067005 No (qualifier value)	
Is patient 709491003 enrolled in Enrollment in clinica	709491003 Enrollment in clinical		Yes	373066001 Yes (qualifier value)	428024001 Clinical trial participant (person)
registred trial?	trial (procedure)		No	373067005 No (qualifier value)	

10.6. SMART risk score

#Last update: 27 - 01 - 2022

smart2 <- function(age, sex, isSmoking, sbp, diabetesDiagnosis, coronaryArteryDisease, cerebrovascularDisease, peripheralArteryDisease, aorticAneurysm, yearsSinceFirstDiagnosis, hdlCholesterol, totalCholesterol, creatinin, crp, hrFutureEvent = 1, usingAnticoag, region){

LP <- NULL tenYearRisk <- NULL

sex <- ifelse(sex==1, "M", "F")</pre>

#Berekenen eGFR obv CKDepi
gfr <- ifelse(sex=="M", 32788*creatinin^(-1.154)*age^(-0.203),
32788*creatinin^(-1.154)*age^(-0.203)*0.742)</pre>

#Berekenen non-HDL obv totaal cholesterol en HDL nonHdl <- totalCholesterol - hdlCholesterol

LP= -0.0349602236 * age + 0.0005510715 * age^2 + ifelse(sex=="M", 0.2876587433, 0) + 0.3455832714 * isSmoking + 0.0018913154 * sbp + 0.3181706587 * diabetesDiagnosis + 0.2947019539 * coronaryArteryDisease + 0.3483178604 * cerebrovascularDisease + 0.3303566308 * aorticAneurysm +

¹⁸ As defined in European Risk Regions (heartscore.org) -Netherland: Low; Austria: moderate; Estonia: High

0.2244665798 * peripheralArteryDisease + 0.0476995851 * yearsSinceFirstDiagnosis -0.0016497342 * yearsSinceFirstDiagnosis^2 + 0.5403642493 * log(nonHdl) -0.0396752081 * gfr + 0.0002186126 * gfr^2 + 0.1517601731 * log(crp) -0.2107210313 * usingAnticoag

tenYearRisk <- 1 - (1-0.1658228)^exp(LP + 0.0463729 - log(ratioRegion)) tenYearRisk <- ifelse(tenYearRisk==1,0.9999999,tenYearRisk)

tenYearRiskWithTreatment <- 1 - (1-tenYearRisk)^(hrFutureEvent) #hrFutureEvent komt uit behandeleffectenscript

return(

) }

```
list(
currentTenYearRisk = tenYearRisk,
tenYearRiskWithTreatment = tenYearRiskWithTreatment
)
```

11. Regulatory, Ethical, and Study Oversight Considerations

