+ 0.3303566308 [if abdominal aortic aneurysm, history or presence of supra- or infrarenal aneurysm of the aorta > 3 cm, or aortic surgery]	 Answer is Y in case of presence of SNOMED: << 233985008 Abdominal aortic aneurysm (disorder) (and all children codes) OR SNOMED: << 67362008 Aortic aneurysm (disorder) (and all children codes) OR SNOMED: << 32907006 Operation on aorta (procedure) (and all children codes) 	Mandatory (default = N)
+ 0.2244665798 [if peripheral artery disease, history or presence of claudicatio intermittens, lowered ankle-arm index or surgical intervention (like angioplasty,	 Answer is Y in case of presence of SNOMED: << 840580004 Peripheral arterial disease (disorder) (and all children codes) OR SNOMED: << 63491006 Intermittent claudication (finding) (and all children codes) OR SNOMED: << 446841001 Ankle brachial 	Mandatory (default = N)

Formulas	SNOMED / LOINC Code (available in PHKG)	Population ¹² value if missing
stenting, endarterectomy, vascular bypass or amputation)]	 pressure index (observable entity) (and all children codes) OR SNOMED: << 387713003 Surgical procedure (procedure) (like <418285008 Angioplasty of blood vessel (procedure)> OR <233434005 Insertion of stent into vein (procedure)> OR <392031002 Endarterectomy (procedure)> OR <116360008 Arterial bypass graft (procedure)> (and all children codes) 	
 + 0.0476995851 x years since first diagnosis of vascular disease + 0.0016497342 x years since first diagnosis of vascular disease A2 	 years (YRS) = current year - Y1 (year of first diagnosis of any of the above 4 diagnosis groups) Y1 = smallest of A,B,C,D where A = year of first occurrence of coronary artery disease B = year of first occurrence of history of cerebrovascular disease C = year of first occurrence of abdominal aortic aneurysm D = year of first occurrence of peripheral artery disease years = YRS as above 	VAL= 1 year
+ 0.5403642493 x log(nonHDL)	 nonHDL = total-cholesterol - HDL-cholesterol WHERE total-cholesterol in mmol/L = Last value LOINC: 14647-2 OR if not available VAL = 4.9 mmol/l HDL-cholesterol in mmol/L = Last value LOINC : 14646-4 OR if not available VAL = 1.2 mmol/l 	For all lab value, if the unit of measurement is different in the ontology that the one in the formula transform with unit needed

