+ 0.0396752081 * eGFR ² (in mL/min/1.73m ² + 0.0002186126 * eGFR ² (in mL/min/1.73m ²) + 0.1517601731 * log(High	Last value LOINC: 62238-1 If not available, derive from creat(SerumCreatine in micromol/l (LOINC = LP145994-2) (per paper Based on Heart. 2013 Jun;99(12):866-72 & Circulation. 2016 Nov 8;134(19):1419-1429 eGFR in mL/min per 1.73 m2 = If patient is male (SNOMED: 248153007) THEN = 32788 * creat ^(-1.154) * age ^(-0.203) ELSE 32788 * creat ^(-1.154) * age ^(-0.203) * 0.742 If the last value of LOINC: 30522-7 is above 15 then	VAL creatine = 92 micromol/l (to be transformed) VAL = 2.2mg/l =
Sensitivity-CRP in mg/dL)	use the previous value (up to the time the value is below 15). If there is no value below 15, then take default	22mg/dL

Formulas	SNOMED / LOINC Code (available in PHKG)	Population ¹² value if missing
+ 0.2107210313 * usingAnticoag	 Answer is Y in case of presence of one or more drugs of category Platelet aggregation inhibitors excl. Heparin (ATC = B01AC) OR A combination of One or more drugs of category Platelet aggregation inhibitors excl. Heparin (ATC = B01AC) + one or more drug of category Direct factor Xa inhibitors (ATC = B01AF) 	VAL = Y
	 Example: can be Ascal, aspirin or an other equivalent (AAS, carbasalate calcium) Dual antiplatelet therapy : Ascal / aspirin + a P2Y12 inhibitor Direct oral anticoagulants (DOAC) P2Y12 inhibitor Ascal / Aspirin + low dose direct working oral anticoagulation (DOAC) 	

In case of missing data, some parameters can use population average value as indicated in the last column. If a mandatory value is missing, the default value indicated in the last column will be used. Note: it is expected that birthdate, gender and systolic blood pressure will be available. The score will be computed by AIDAVA and by the treating (junior) physician. It will then be checked by the senior physician; in case of discrepancy between the score computed by AIDAVA and by the physicians, the senior physician will require explanations on how AIDAVA came to the different answers/codes needed to compute the score and decide the reason for discrepancy.

The senior physicians will be presented with a table with all the parameters used to compute the score (as displayed in the figure below) and be able to get information on how AIDAVA came to a certain value (which data source, which transformation).

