- Alternative hypothesis (H2 CVD): AIDAVA G1 provides an accurate SMART score (accuracy of 80%+) on patients, across sites, without any time spent by CVD specialists. G2 has similar or better results.

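### The default CRP in the SMART specification is printed as 2.2 mg/l = 22 mg/dL (2.2 mg/l is 0.22 mg/dL), and the code in Section 10.6 gives no unit that would settle which value belongs in the score

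*Protocol*

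**What the plan says.** The technical specification of the SMART score in Protocol Section 3.2.2 has a CRP term that begins "0.1517601731 * log(High" and continues "Sensitivity-CRP in mg/dL". So the formula is labelled in mg/dL. The last column of that row holds the value to use if CRP is missing. Read across a split cell, it says that 2.2 mg/l equals 22 mg/dL.

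The row also screens high values: "If the last value of LOINC: 30522-7 is above 15 then" the previous value is used, going back until one is below 15. "If there is no value below 15, then take default". The 15 carries no unit. For missing data the section says: "In case of missing data, some parameters can use population average value as indicated in the last column".

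A unit rule for all laboratory values stands in the cholesterol row of the same table: "if the unit of measurement is different in the ontology that the one in the formula transform with unit needed".

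Section 10.6 prints the R code for the score. Its CRP term is "0.1517601731 * log(crp"), with the same coefficient and no unit for the argument.

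Section 9.1 sets the hypothesis for the cardiovascular use case: "AIDAVA G1 provides an accurate SMART score (accuracy of 80%+) on patients, across sites". Section 3.2.2 (Metric 2) defines accuracy by comparing the AIDAVA score with the score that the physician obtains, using the U-Prevent web calculator.

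**The concern.** The printed equality is false, and it stands in the table from which the score is to be programmed. Someone who follows the table literally uses mg/dL because the formula says so. A measured 2.2 mg/l is then converted to 0.22, while a missing value is filled with 22. Two patients with the same CRP would receive different scores, depending only on whether the value was found.

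Section 10.6 cannot correct this. The code gives no unit, so 0.22, 2.2 and 22 are all admissible as far as it shows.

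At stake is the secondary cardiovascular Metric 2. The physician's score comes from a separate web calculator, and nothing says that the physician uses the 22. A wrong default could therefore be counted as AIDAVA inaccuracy even where extraction was faultless. The reasons for discrepancy that Section 3.2.2 offers the senior physician are an incomplete record, an AIDAVA error and a physician error. None covers a faulty specification.

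**Working it through.** **Inputs from the documents.** Coefficient b = 0.1517601731 (Sections 3.2.2 and 10.6); default 2.2 mg/l, printed as 22 mg/dL (3.2.2); risk function 1 − (1 − 0.1658228)^exp(LP + 0.0463729 − log(ratioRegion)) (10.6). In R, log is the natural logarithm.

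**Inputs assumed.** True 10-year risk of 20% for illustration, varied from 5% to 40%. The documents give no such figure.

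**The plan's own figure.** One litre is 10 dL, so 2.2 mg/l = 2.2/10 = 0.22 mg/dL. The printed 22 does not reproduce: 22/0.22 = 100.

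**Effect on the score.** A CRP wrong by a factor k adds b·ln(k) to the linear predictor. That multiplies the hazard by k^b, and a true risk p becomes 1 − (1 − p)^(k^b). The formula in 3.2.2 also has the linear predictor inside exp() as a power of a baseline survival, so this step does not depend on which baseline constant is used.

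- 22 entered, coefficient per mg/l (2.2 correct, k = 10): 10^0.15176 = 1.418
- 22 entered, coefficient per mg/dL (0.22 correct, k = 100): 100^0.15176 = 2.012

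| Assumed true risk | Score, k = 10 | Score, k = 100 |
|---|---|---|
| 5% | 7.0% (+40%) | 9.8% (+96%) |
| 10% | 13.9% (+39%) | 19.1% (+91%) |
| 20% | 27.1% (+36%) | 36.2% (+81%) |
| 30% | 39.7% (+32%) | 51.2% (+71%) |
| 40% | 51.5% (+29%) | 64.2% (+61%) |

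For 20%: 1 − 0.8^1.418 = 0.271 and 1 − 0.8^2.012 = 0.362.

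**If 2.2 is entered instead.**

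- Coefficient per mg/l: the default is right and causes no error.
- Coefficient per mg/dL: 2.2 stands where 0.22 belongs, so the hazard is still 1.42 times too high.

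**Measured values.** If the coefficient is per mg/l but measured mg/l values are converted to mg/dL, as the table orders, they enter 10 times too small. The multiplier is 10^−0.15176 = 0.705, and 1 − 0.8^0.705 = 0.146. An assumed 20% becomes 14.6% (−27%).

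**Default against measured, following the text literally.** With 0.22 for a measured 2.2 mg/l and 22 for a missing one, the hazards differ by 100^0.15176 = 2.01, whichever unit the coefficient belongs to.

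**Example with the 10.6 code.** Inputs: man aged 60, non-smoker, coronary disease, no diabetes, systolic pressure 140, the 3.2.2 defaults for the rest (cholesterol 4.9 and 1.2, creatinine 92, 1 year, antithrombotic yes), and ratioRegion set to 1 because its value is not shown. The score is 8.9% at CRP 0.22, 12.3% at 2.2 and 17.0% at 22.

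**The case against.** - **The cell is split, and the text was read by a program.** A leading 0 and decimal point may have been lost, so the original must be checked. Even if it reads 0.22, the 10.6 code still has no unit and the cut-off of 15 still has none.
- **The code in 10.6 contains no arithmetic error.** This is correct. The wrong figure stands in 3.2.2; 10.6 only fails to resolve it.
- **The cell gives 2.2 mg/l first.** A programmer may enter 2.2. A reader might infer that every patient on the default is over-scored by a third to four fifths. The documents do not support that: it needs 22 to be the number entered and a true risk near 20%.
- **Rejection does not lead straight to the default.** A reader might infer that any value above 15 is replaced by 22. The rule first goes back to an earlier value below 15. Comparing the unit-less 15 with 22 mg/dL also shows no contradiction separate from the conversion error.
- **A senior physician reviews discrepancies and sees every parameter with its source.** A CRP of 22 would be visible there. That helps to explain a discrepancy, but nothing says that it changes the recorded accuracy.
- **The physician may also lack a CRP.** What the web calculator then does is not shown, so the effect on Metric 2 is possible but not established.
- **The 80% target.** A reader might infer that these errors miss it. Section 9.1 does not say whether 80% is a limit on each patient's deviation or a share of patients, so a 20% allowance is only one reading.
- **G1 against G2.** A reader might infer that G2 will look better merely because fewer defaults are used. Finding more CRP values would also be better extraction, which the study means to measure, and the documents give no default rate for either generation.

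**Conclusion.** The point holds in a conditional form. As printed, the default in the formula's stated unit is 100 times too high, and neither 3.2.2 nor 10.6 settles which number belongs in the score.

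If 22 is entered, the over-score across assumed true risks of 5% to 40% is +29% to +40% (coefficient per mg/l) or +61% to +96% (per mg/dL). If 2.2 is entered with a per-mg/l coefficient, the default is harmless, but the ordered conversion of measured values would then produce an under-score.

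The size rests on the assumed true risk and on which number is programmed. How many of the 45 cardiovascular patients would take the default is unknown. The endpoint is secondary, and the protocol states that the prototype is not used for clinical decisions. This is a specification error to correct before scoring; it does not threaten the study's primary comparison.

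**What to change.** Before any score is computed:

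1. Check the original table cell in Section 3.2.2.
2. Confirm with the owner of the 10.6 code which CRP unit the coefficient belongs to.
3. State that one unit for the coefficient, the default and the cut-off of 15, in both 3.2.2 and 10.6. The default is then 2.2 if the unit is mg/l, or 0.22 if it is mg/dL. Delete 22 mg/dL.
4. Make sure that AIDAVA converts measured values to the same unit.
5. Enter one test patient in both AIDAVA and the web calculator, and confirm that the scores agree.

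The cost is one corrected table row, one comment in the code and one test entry. No patients or visits are added.

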11.1 Regulatory and Ethical Considerations

From an ethical point of view, the AIDAVA-curated data will NOT be presented to clinicians and patients as being reliable for final use, but as a research prototype output to be validated before use (if they choose to) in the care process or clinical research activities.

The partners intend, provided that this project demonstrates success, to obtain Medical Device Regulation certification so that the outputs can be accepted and used. This will only occur after the project.

- This study will be conducted in accordance with the protocol and with the following:
 - Consensus ethical principles derived from international guidelines including the Declaration of Helsinki and Council for International Organizations of Medical Sciences (CIOMS) international ethical guidelines
 - Applicable ICH Good Clinical Practice (GCP) guidelines
 - Applicable laws and regulations
- The protocol, protocol amendments, ICF, SIP will be submitted to an IRB/IEC by the investigator and reviewed and approved by the IRB/EC active in each of the study centres, before the study is initiated.
- Any amendments to the protocol will require IRB/EC approval before implementation of changes made to the study design, except for changes necessary to eliminate an immediate hazard to study participants.

